IWRS	Interactive Web Randomization System

This document is confidential.

Abbreviation	Description
ICH	International Conference on Harmonization
LLOQ	Lower Limit of Quantification
LRTI	Lower respiratory tract illness
MAAE	Medically-Attended Adverse Event
MedDRA	Medical Dictionary for Regulatory Activities
N/A	Not Applicable
NAb	Neutralizing Antibody
pIMC	Potential Immune-Mediated Condition
PPS	Per Protocol Set
PT	Preferred Term
RCD	Reverse Cumulative Distribution
RCDC	Reverse Cumulative Distribution Curve
RSV	Respiratory Syncytial Virus
SAE	Serious Adverse Event
SAP	Statistical Analysis Plan
SD	Standard Deviation
SMC	Safety Monitoring Committee
SNA	Serum Neutralization Assay
SRR	Seroresponse Rate
SOC	System Organ Class
SOP	Standard Operating Procedure
TFL	Table, Figure and Listing
VLP	Virus-like Particle

This document is confidential.

2. Purpose

The statistical analysis plan (SAP) is developed under the protocol version 5.0 dated 02 April 2024 in concert with subsequent notification that the open label extension of the trial (in protocol version 5.0) was discontinued by the Sponsor (October 2024). The purpose of this SAP is to ensure that the data listings, summary tables and figures which will be produced, and the statistical methodologies which will be used, are complete and appropriate to allow valid conclusions regarding the study objectives.

2.1. Responsibilities

Syneos Health will perform the statistical analyses and is responsible for the production and quality control of all derived datasets, and tables, figures and listings.

2.2. Timings of Analyses

An independent safety monitoring committee (SMC) will be constituted to monitor the safety of all subjects enrolled in the trial, including solicited local adverse reactions (ARs), solicited systemic ARs, unsolicited adverse events (AEs), and clinical laboratory data. The SMC will review safety data collected during the 7 consecutive days following vaccination for all subjects, focusing on the interpretation of solicited local ARs and solicited systemic ARs, unsolicited AEs and clinical laboratory data in the first week after dosing when most reactogenicity is expected to occur. Details of the membership, roles and functioning of the committee will be available in the SMC charter.

Further description of the SMC analyses can be found in the SMC charter. The SMC charter was authored by Icosavax Inc. For the closed SMC session, an unblinded team from Syneos Health Biostatistics will perform the analyses as described in [Section 4.4](#) of this SAP to maintain the blinding of the trial.

Two interim analyses (IA) will be performed: the first when all subjects have completed the Day-28 safety assessments and all Day-28 immunogenicity data are available; the second when all subjects have completed the Day-180 safety assessments and all Day-180 secondary immunogenicity data are available. These analyses will support further evaluation of safety and immunogenicity of IVX-A12 in older adults. The purpose of the interim analyses will be used for confirmation of dosage level and formulation selected for further evaluation in older adults 60 years of age or older. For each of the interim analyses, a data-cut will be performed. For the Day-28 interim analysis, all data through day 28 will be included. For the Day-180 interim analysis, all data through day 180 will be included. Additional details regarding the data cut will be found in the *Data Cut-Off Guidance* document.

A primary analysis is planned after all subjects complete the final trial visit, Day 365, or terminate early from the trial and all data is available. The open label extension of the trial starting after Visit Day 365 was discontinued early, prior to the subjects completing Day 545. The limited amount of data from the extension will be reported once all data are available.

This document is confidential.

3. Study Objectives

3.1. Main Trial Objectives

3.1.1. Primary Safety Objective

The primary safety objective is to assess the safety and tolerability of IVX-A12 bivalent candidate vaccine with or without MF59 adjuvant compared to placebo up to 1 year following a single IVX-A12 vaccination when administered as a single-dose regimen in healthy older adults 60 to 85 years of age.

3.1.2. Primary Immunogenicity Objectives

The primary immunogenicity objectives are as follows:

- To evaluate the serum Neutralizing Antibody (NAb) responses to IVX-A12 +/- MF59 or placebo, measured by live virus serum neutralization assays (SNA), at Day 28.
- To evaluate the serum immunoglobulin G (IgG) binding antibody response to IVX-A12 or placebo, measured by enzyme-linked immunosorbent assays (ELISA), at Day 28.
- To evaluate the proportion of subjects with a ≥ 4 -fold increase in serum NAb and serum IgG binding antibody titers to IVX-A12 from prevaccination/baseline (Day 0) to Day 28.

3.1.3. Secondary Safety Objective

[figure not shown]
The secondary safety objective is to assess the safety of IVX-A12 compared to placebo by the incidence of serious adverse events (SAEs), adverse events of special interest (AESIs) (which were defined as potential immune-mediated conditions (pIMCs)), medically-attended adverse events (MAAEs), clinical event of special interest (CESIs) (which were defined as lower respiratory tract illness (LRTI) cases of any severity (mild, moderate, severe) caused by RSV and/or hMPV), LRTI cases of any severity (mild, moderate, severe) not caused by RSV or hMPV, and AEs leading to trial withdrawal up to Day 365 (end of the main trial).

3.1.4. Secondary Immunogenicity Objectives

The secondary immunogenicity objectives are as follows:

- To evaluate the serum NAb response to IVX-A12 or placebo at Day 0, Day 180, and Day 365
- To evaluate the serum IgG binding antibody response to IVX-A12 or placebo at Day 0, Day 180, and Day 365 after vaccination.
- To evaluate the proportion of subjects with a ≥ 4 -fold increase in serum NAb and serum IgG binding antibody titers at Day 180 and 365 compared to baseline (Day 0).
- To evaluate the proportion of subjects with an ≥ 8 -fold increase in serum NAb and serum IgG binding antibody titers at Day 28, Day 180 and Day 365 compared to baseline (Day 0).

CCI

This document is confidential.

CCI

3.2. Observational Extension Objectives

3.2.1. Primary Objective

There are no primary objectives for the observational extension portion of the trial.

3.2.2. Secondary Safety Objective

The secondary safety objective, for the observational extension trial, is to describe the incidence of SAEs, AESIs, and MAAEs in consenting IVX-A12a vaccinees and placebo recipients through an additional 12 months (Day 730).

Note: given the observational extension portion of the trial was discontinued, these data will only be included in a listing through time of subject discontinuation.

CCI

This document is confidential.

4. Study Details/Design

4.1. Brief Description

4.1.1. Main Trial Brief Description

The Phase 2a clinical trial of IVX-A12 is a randomized, observer-blind, placebo-controlled, dosage optimization, multi-center trial to evaluate the safety and immunogenicity of a single IM dose of two different formulations of IVX-A12 (IVX-A12a with diluent alone and IVX-A12d with MF59[®]) compared to placebo (diluent) in adults 60 to 85 years of age. The dosage level and formulation were selected based on the totality of the IVX-A12 nonclinical data and the interim safety and immunogenicity clinical data from the ongoing IVX-A12 Phase 1 clinical trial.

The main portion of this Phase 2a clinical trial will have three vaccine groups: Two IVX-A12 groups and one placebo group. The total amount of VLP in the two IVX-A12 groups will not exceed 300 µg of VLPs. IVX-A12a, IVX-A12d, or placebo will be administered as a single IM dose to older adult subjects enrolled into two age strata (adults 60 to 69 years of age and elderly adults 70 to 85 years of age). Eligible older adults will be randomized simultaneously to the different trial groups to ensure balance among the groups. This Phase 2a clinical trial includes a sentinel group of 40 subjects (16 subjects per active treatment group [n=32]; 8 subjects in the placebo group) to conservatively assess the 150 µg RSV/150 µg hMPV dosage level in combination with MF59[®]. Sentinel subjects were closely monitored for a minimum of 48 hours and, if no stopping rules were triggered, the remaining subjects were enrolled.

Approximately 250 subjects will be randomly allocated at a ratio of 2:2:1 to receive one of the two IVX-A12 formulations (IVX-A12a [N=100] or IVX-A12d [N=100]) or placebo (N=50), respectively. Subjects were also be stratified by age group (60 to 69 years of age and 70 to 85 years of age). The planned subject allocation to trial groups is provided in [Table 1](#).

Table 1

Group	Dosage Level	Total (N=250)*
A	IVX-A12a (unadjuvanted 150 µg RSV/ 150 µg hMPV)	100
B	IVX-A12d (150 µg RSV/ 150µg hMPV adjuvanted with MF59 [®])	100
C	Placebo [†]	50

[†] Placebo will be aqueous diluent

*Note: The stratified randomization will ensure balanced dosage level group assignment between the two age groups (60 to 69 years of age and 70 to 85 years of age, respectively).

4.1.2. Observational Extension Trial Brief Description

Eligible IVX-A12a and placebo recipients will be invited to enroll into the observational extension portion of the trial, which includes a telephone call at Day 545 (approximately 6 months from Day 365) and a clinic visit at approximately 12 months (Day 730) after the Day 365 visit for a final blood draw. The upper age limit of 85 years was removed.

The observational extension portion of the trial discontinued early, prior to the subjects completing Day 545.

This document is confidential.

4.2. Subject Selection

Adults 60-85 years of age will be enrolled. Inclusion and exclusion criteria are described in the protocol in Sections 7.1 and 7.2, respectively.

4.3. Determination of Sample Size

4.3.1. Main Trial Determination of Sample Size

Sample size for this trial is not based on any formal hypothesis testing. Analyses of safety and immunogenicity will be primarily descriptive in nature. An approximate total of 250 subjects (approximately 100 subjects in each of the IVX-A12 groups and 50 subjects in the placebo group) will be randomized. With 100 subjects in each IVX-A12, there is a 63.4% probability of observing at least 1 subject with an AE if the true incidence of the AE is 1% and 86.7% probability of observing at least 1 subject with an AE if the true incidence of the AE is 2%. The trial will have more than 90% power to detect a difference of 20% or more in seroresponse rate (SRR) or detect a 2-fold increase or more in GMT or GMFR (assuming standard deviation at $0.5 \log_{10}$), between the two IVX-A12 groups (or between the IVX-A12 group and placebo group), with a two-sided type-1 error rate at 0.05.

4.3.2. Observational Extension Trial Determination of Sample Size

Enrollment is based on subject consent, interest, eligibility, and prior vaccination receipt (IVX-A12a or placebo) to continue in the observational extension trial. No sample size is calculated for the observational extension trial.

4.4. Vaccine Group Assignment and Blinding

Only subjects who have a signed informed consent form (ICF) and meet all of the inclusion criteria and none of the exclusion criteria are eligible for randomization and assignment to a vaccine group. The randomization specification will be approved by the sponsor's trial statistician, or designee. Subject randomization will be conducted using an interactive web randomization system (IWRs). The system will ensure proper distribution of subjects across trial groups at each strata.

The Syneos Health (SYNH) blinded team will include a Lead Biostatistician, SDTM programmers, ADaM/TFL programmers as well as a Senior Reviewing Statistician. A separate unblinded team will work independently of the blinded team to receive, review, and manage the unblinded data. The unblinded team--including unblinded statisticians and unblinded programmers--do not have any day-to-day roles in the conduct of the trial.

The IAs and any SMC will occur while the trial is still blinded. Unblinded outputs during the course of the trial will be presented to the SMC in a fully unblinded fashion for vaccine groups in summaries, and listings will be presented by vaccine group. A list of IA outputs is maintained in the document *ICVX-12-201 Interim Analysis Tables Listings Figures*.

The blinded team will develop and validate the SAS programs necessary for analysis on the blinded data. Once validated, the unblinded programming team members will run the SAS programs on the unblinded trial data in a secure, access-restricted area. The unblinded statistician will review the outputs produced by the unblinded team. For the SMC, unblinded outputs will be distributed via Cocinnity in an unblinded area for the SMC, where only unblinded members have access. Otherwise, unblinded outputs will be distributed via Egnyte in an unblinded area, where only unblinded members have access.

This document is confidential.

Data with the potential to unblind will be available to the blinded team only in a blinded fashion. Any potentially unblinding information would be masked prior to hand-off to the blinded team.

The main trial will remain blinded until database lock for the primary analysis at Day 365, except for subjects who will receive a letter with their treatment assignment at their Day 365 visit. Blinded Clinical Research Associates and the Blinded Clinical Lead will also be unblinded at the end of each Day 365 visit. The remaining team members will remain blinded until every subject has completed their Day 365 visit and the Day 365 database has been locked. At the time of primary analysis, the SYNTH blinded biostatistics team will become unblinded. For further details, reference the Unblinded Team Management Plan.

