8.3 Randomization Code Creation and Storage

Randomization is conducted using an IWRS. The system ensures proper distribution of subjects across group assignments; treatment assignments known only to the responsible unblinded trial personnel/vaccine administrators at the study center. Subjects and the main study team and clinical staff will remain blinded for the duration of the study unless emergency unblinding is necessary.

Randomization information is stored in a secured area, accessible only by authorized personnel.

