8.5 Unblinding Procedure

The IMP blind shall not be broken by the investigator unless information concerning the IMP is necessary for the medical treatment of a subject, or if a subject requests it. In the event of a medical emergency, if possible, the medical monitor should be contacted before the IMP blind is broken to discuss the need for unblinding.

For unblinding a subject, the IMP blind can be obtained by the investigator, by accessing the IWRS.

The L pharmacovigilance department must be notified as soon as possible if the IMP blind is broken by the investigator and the completed SAE form, if applicable, must be sent within 24 hours. The date, time, and reason the blind is broken must be recorded in the source document.

If any subject is unblinded, the subject should continue to be monitored for safety follow-up.

All subjects will be unblinded at their Day 365 visit.

8.6 Accountability and Destruction of Sponsor-supplied Investigational Medicinal Products, and Other Clinical Trial Materials

The investigator or designee must ensure that the sponsor-supplied IMP are used in accordance with the approved protocol and is administered only to subjects enrolled in the trial. To document appropriate use of sponsor-supplied IMP, the investigator must maintain records of all sponsor-supplied IMP delivery to the site, site inventory, administration and use by each subject, and destruction or return to the sponsor or designee.

The investigator must maintain 100% accountability for all sponsor-supplied IMPs and other CTM (including ancillary materials, as applicable) received and administered during their entire participation in the trial. Inventory, tracking and accountability forms will be maintained in the pharmacy files.

Prior to site closure or at appropriate intervals throughout the trial, before any IMP, or CTM are destroyed or returned to the sponsor or designee for destruction, a representative from the sponsor will perform CTM accountability and reconciliation.

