13.0 STATISTICAL METHODS

13.1 Statistical and Analytical Plans

A statistical analysis plan will be prepared and finalized prior to unblinding of the trial groups. This document will provide further details regarding the definition of analysis variables and analysis methodology to address all trial objectives.

A (blinded) data review will be conducted prior to unblinding of the trial groups. This review will assess the accuracy and completeness of the trial database, subject evaluability, and appropriateness of the planned statistical methods.

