6.1.5. Per Protocol Set

The Per Protocol Sets (PPS) will include all subjects in the FAS who received a dose of IVX-A12 or placebo and have no major protocol deviations, which may exclude subjects from PPS. Subjects will be analyzed according to randomized group. If a subject has a major protocol deviation or RSV/hMPV infection after Day 28, their post-Day 28 data point may be excluded. Blinded data review meeting (BDRM) will be conducted prior to each Interim Analysis and prior to data base lock and unblinding of the vaccine groups. During the BDRMs, a final decision (sponsor call) will be taken as to which subjects/visit will be excluded.

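### The CRAs and the Clinical Lead learn individual assignments at Day 365, before the last nominally blinded review at which the sponsor makes discretionary per-protocol exclusions

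*SAP*

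**What the plan says.** Protocol 13.1: "A (blinded) data review will be conducted prior to unblinding of the trial groups". Subject evaluability is one of the things that review is to assess.

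Protocol 8.3: "Subjects and the main study team and clinical staff will remain blinded for the duration of the study unless emergency unblinding is necessary". Protocol 8.5, however: "All subjects will be unblinded at their Day 365 visit".

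SAP 4.4 keeps the main trial blinded until lock for the Day 365 analysis, with exceptions. Subjects receive a letter with their assignment at the Day 365 visit, and "Blinded Clinical Research Associates and the Blinded Clinical Lead will also be unblinded at the end of each Day 365 visit". For everyone else, "The remaining team members will remain blinded until every subject has completed their Day 365 visit and the Day 365 database has been locked".

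SAP 6.1.5 covers the exclusions. On timing: "Blinded data review meeting (BDRM) will be conducted prior to each Interim Analysis and prior to data base lock and unblinding of the vaccine groups". On who decides: "During the BDRMs, a final decision (sponsor call) will be taken as to which subjects/visit will be excluded". On later data: "If a subject has a major protocol deviation or RSV/hMPV infection after Day 28, their post-Day 28 data point may be excluded".

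SAP 9.1 and 11.1 make the PPS the default set for immunogenicity and for exploratory efficacy.

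**The concern.** A review that decides who is evaluable protects the randomised comparison only if the people who inform and make the decision do not know the assignments. Here two study-team roles learn them one subject at a time, while exclusions affecting the Day 365 analysis are still open.

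The decision also leaves room for judgement. SAP 6.1.5 makes exclusion of later data optional and does not list the deviations that lead to exclusion. SAP 6.3 classes a deviation as major if it could affect safety or the primary and secondary endpoints, while protocol 13.1.1 asks for a significant effect on immunogenicity results. SAP 9.1.2 plans displays of late fold-rises to find unrecognised infections, without saying whether such a finding can lead to exclusion.

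At stake is whether the Day 365 per-protocol results can be presented as resting on blind exclusions. No immunogenicity summary on the Full Analysis Set (FAS) is planned, only listings, so a reader of the report could not see what the exclusions did.

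**Working it through.** The plan gives no figure for this point. The check is the order of events.

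| Step | Source | Who knows individual assignments |
|---|---|---|
| BDRM before the Day 28 interim analysis | SAP 6.1.5 | Not yet the CRAs or the Clinical Lead |
| BDRM before the Day 180 interim analysis | SAP 6.1.5 | As above, provided it precedes the first Day 365 visit |
| Each Day 365 visit | SAP 4.4; protocol 8.5 | That subject, the CRAs and the Clinical Lead |
| Last BDRM, before lock | SAP 6.1.5 | As above, for every subject already seen at Day 365 |
| Lock, then primary analysis | SAP 2.2, 4.4 | The remaining team, from lock |

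The position of the fourth row is an inference. SAP 2.2 places the primary analysis after all Day 365 visits, and a review that is to settle Day 365 samples and infections up to Day 365 needs those data.

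**Against protocol 8.3.** The only exception there is emergency unblinding. The planned unblinding of the CRAs and the Clinical Lead in SAP 4.4 is not an emergency, so the two texts conflict. Protocol 8.3 also conflicts with protocol 8.5 as regards the subjects themselves.

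**Against protocol 13.1.** The review is to be blinded and to precede unblinding of the trial groups. Once two team roles know individual assignments, that holds only if they take no part. The SAP text does not say so.

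**Which data are exposed.**
- Day 28 and Day 180: exclusions were first settled at the BDRMs before each interim analysis. They are exposed only if reopened; the SAP neither provides for reopening nor rules it out.
- Day 365 immunogenicity, late exclusions for infection or deviation after Day 28, and PPS membership for efficacy: decided, or still open, after unblinding began.

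**Scale, for illustration only.** If a fraction f of one arm is excluded and its mean log10 titer differs by d from those retained, the arm's GMT changes by the factor 10^(f × d). Take d = 0.5, equal to the SD in SAP 4.3.1:
- f = 0.05: 10^(0.05 × 0.5) = 10^0.025 = 1.059, a shift of about 6%.
- f = 0.10: 10^(0.10 × 0.5) = 10^0.05 = 1.122, a shift of about 12%.

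The extreme case drops only the lowest titers in one arm (normal log10 titers, SD 0.5, 40,000 simulated replicates):

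| Lowest titers dropped | Arm of 100 | Arm of 50 |
|---|---|---|
| 1 | GMT up about 3% | up about 5% |
| 3 | up about 8% | up about 15% |
| 5 | up about 13% | up about 24% |

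Both f and d are assumptions. The extreme case also needs the excluded subjects to be chosen on titer, and knowing the arm does not reveal the titer.

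**The case against.** The strongest reply is that the documents show a sequence, not a route to bias.

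- **Role at the review.** A reader might infer that the CRAs and the Clinical Lead attend the last BDRM or supply the deviation record. The documents do not support that. SAP 6.1.5 gives the decision to the sponsor, SAP 6.3 says only that deviations are held in the CTMS, and neither document lists attendees or says who employs the Clinical Lead. SAP 4.4 also refers to an Unblinded Team Management Plan, which may restrict these roles. This stands: the finding is a gap in the SAP text, not evidence of unblinded decisions.
- **Protocol 13.1.** A reader might call this a plain breach. But 13.1 and SAP 6.1.5 speak of unblinding the groups, and most of the team stays blinded until lock. The commitment is weakened, not clearly broken. The direct conflict is with protocol 8.3.
- **Day 28 co-primary results.** A reader might infer that these are biased. They had their own blinded review before the interim analysis, and the optional-exclusion sentence concerns data after Day 28. Protocol 6.3 and 7.3 also presuppose that per-protocol status is known at Day 365. This stands.
- **Limited discretion.** Out-of-window samples are excluded by rule (SAP 7.5), the LRTI case definition requires RT-PCR confirmation (protocol 10.1.3), and cases are derived by program and also tabulated on the Safety Set (SAP 10.1). All analyses are descriptive, so no type I error claim is affected. This narrows the exposure but leaves subject- and visit-level exclusions to judgement.

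None of this removes the conflict with protocol 8.3, or supplies the missing statement of who may take part in the last review.

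**Conclusion.** The point holds as a conflict between documents and a missing safeguard. The plan's own unblinding rule undercuts a review that it calls blinded, and the exclusions made there are discretionary. The exposure is mainly Day 365 immunogenicity, late exclusions for infection or deviation after Day 28, and exploratory efficacy. For the Day 28 co-primary endpoints it is conditional on reopening decisions already taken blind.

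The size of any bias cannot be estimated, because the documents give no exclusion counts. The percentages above show how a GMT responds to assumed exclusions; reading them as expected bias would go beyond the documents.

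The conclusion rests on two assumptions: that the last BDRM follows the Day 365 visits, and that no unseen document already limits who takes part. If the Unblinded Team Management Plan does so, what remains is to say it in the SAP and to reconcile SAP 4.4 with the protocol.

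**What to change.** In SAP 6.1.5, state that:

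1. PPS decisions for Day 28 and Day 180 stand as signed at the BDRM before each interim analysis.
2. Only staff still blinded to individual assignments take part in exclusion decisions at the last BDRM.
3. Any exclusion added or changed after the first Day 365 unblinding is documented with date and reason, and its effect is shown by a sensitivity analysis without that change, for example on the FAS.

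Then reconcile SAP 4.4 with protocol 8.3 and 13.1.

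The SAP postdates the October 2024 discontinuation of the extension, so the last BDRM may already have taken place. If so, the report should give the attendees' roles and blinding status and list the exclusions changed after the first Day 365 unblinding.

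Two stronger measures are not recommended. Recording exclusions before each subject's treatment letter is impractical, since the subject is unblinded at the visit where the serology is drawn, and it is too late for those already unblinded. Barring anyone aware of group-level interim results would remove the sponsor, who used the Day 28 results to choose the formulation, and such knowledge does not reveal individual assignments.

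The cost is SAP wording plus one sensitivity analysis, using staff who remain blinded under SAP 4.4. The downside is that deviations found late for Day 28 or Day 180 are handled only in the sensitivity analysis.
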